#### **7.4.1.3. Serious Adverse Events**

The investigator must report an SAE to Revance or the designee's authorized representative within 24 hours of their awareness of the event:

1. Complete and return an SAE Form with all information known to date; including the investigator's assessment of causality
2. Contact Revance or the authorized representative for a fatal or life-threatening event as soon as the investigator or study staff are aware of the event
3. Obtain and maintain all pertinent medical records (e.g., discharge summary, autopsy report) and medical judgments of medical personnel who assisted in subject's treatment and follow-up
4. Provide follow-up information to Revance or designee within 24 hours of awareness

Regulatory Authorities, IRBs/ IECs, and investigators will be notified of SAEs in accordance with applicable regulations and requirements (e.g., ICH-GCP, national regulations and local requirements).

#### **7.4.1.5. Follow-up of Non-Serious Adverse Events**

All AEs that are identified during the last scheduled study visit (or the Final Evaluation Visit, if applicable) must be recorded on the AE eCRF as ongoing.

Any clinically significant abnormal test results, (e.g., laboratory findings), at the final assessment should be followed to resolution or until determined by the investigator to be stabilized. Repeat tests may be indicated to establish this.

If a subject has any clinically significant, study-related abnormalities at the end of the study, the Medical Monitor should be notified and every effort made by the investigator to arrange follow-up evaluations at appropriate intervals to document the course of the abnormalities unless the Medical Monitor determines that follow-up is sufficient.

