#### 7.2.4. Follow-up Visits

At Weeks 2, 4, 8, 12, 16, 20, 24, 28, and 32, the following procedures must be performed and recorded:

2. Conduct patient education: discuss the potential effect of DAXI for injection treatment, explain the PFWS, PFHWS, and PLCWS measurement and the categories of the severity assessment scales, and instruct the subjects to consider depth of lines for severity grading. Use the provided Patient Education Brochure.

14. Collect blood and urine samples for clinical safety laboratory tests (hematology, serum chemistry, and urinalysis) (Week 4 Visit only).

17. Assess any new or ongoing AEs since the last visit.

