#### **7.4.1.2. Assessment and Reporting Requirements**

The investigator will assess each subject post-treatment and at each subsequent study visit for the occurrence of AEs. In order to avoid bias in eliciting AEs, subjects should be asked the following non-leading question: "How have you felt since your last visit?" All AEs (serious and non-serious) will be collected from the signing of the ICF until the Final Evaluation Visit. Any AE reported by the subject must be recorded on the source documents and eCRFs.

All AEs will be collected after IP administration until Week 36 or the Final Evaluation Visit at all timepoints as specified in the SOA ([Section 1.3](#)). Medical occurrences related to protocol-mandated intervention that begin before the start of study intervention but after obtaining informed consent will be recorded as AEs.

[figure not shown]
All SAEs will be recorded and reported to Revance or designee immediately within 24 hours of their awareness of the event. All fatal or life-threatening SAEs should be telephoned to Revance or the designee's authorized representative as soon as the investigator learns of the event.

[figure not shown]

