#### **7.4.1.6. Follow-up of Post-Study Serious Adverse Events**

Any SAEs that are identified on the last scheduled contact (or at early discontinuation, if applicable) must be recorded on the AE eCRF and reported to Revance or designee according to the reporting procedures outlined in [Section 7.4.1.2](#). This may include unresolved previously reported SAEs or new SAEs. The investigator should follow these SAEs until the events are resolved, or the subject is lost-to-follow-up. The investigator should continue to report any significant follow-up information to the Medical Monitor, Revance or designee and the IRB/IEC up to the point the event has been resolved. Resolution means the subject has returned to the baseline state of health, or the Investigator does not expect any further improvement or worsening of the subject's condition.

Any new SAEs reported by the subject to the investigator that occur after the last scheduled contact and are determined by the investigator to be reasonably associated with the administration of investigational product should be reported to Revance or designee and the IRB/IEC.

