#### **8.3.2. Safety Analyses**

Adverse events (AEs) occurring during the study will be recorded and classified according to MedDRA terminology. Those occurred one or after treatment are considered as treatment emergent. All reported TEAEs will be summarized, in terms of the number of subjects reporting events, system organ class, preferred term, severity, relationship to study drug, outcome, action taken and seriousness. For summarization of event causality and seriousness, subjects will be counted only once within a system organ class or preferred term using the event with the event with the greatest relationship for causality and the event with the highest severity. A summary of TEAEs leading to discontinuation will also be provided.

A by-subject listing of any SAEs will be provided and all SAEs will be summarized by severity and relationship to study treatment.

Clinical laboratory test and vital sign results will be summarized by visit and if applicable a shift table will be used to evaluate the shift in status from baseline at each visit. [REDACTED]

[REDACTED] Physical examination, injection site findings, [REDACTED] will be summarized as described in the SAP.

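### Section 7.4.1.5 has every AE identified at the last visit recorded as ongoing, which read literally includes events that have already resolved

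*Protocol*

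**What the plan says.** Protocol Section 7.4.1.5, on follow-up of non-serious AEs, opens with a recording rule for the end of the study. All AEs "identified during the last scheduled study visit (or the Final Evaluation Visit, if applicable) must be recorded on the AE eCRF as ongoing". The sentence is complete and has no qualifier such as unresolved or still present.

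Section 7.4.1.2 sets how AEs are elicited. The subject is asked "How have you felt since your last visit", and "Any AE reported by the subject must be recorded on the source documents and eCRFs". Collection has a fixed end: "All AEs will be collected after IP administration until Week 36 or the Final Evaluation Visit".

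For the follow-up visits before the last one, Section 7.2.4 asks the site to "Assess any new or ongoing AEs since the last visit", with no status fixed in advance. The parallel rule for serious events in Section 7.4.1.6 is "Any SAEs that are identified on the last scheduled contact (or at early discontinuation, if applicable) must be recorded on the AE eCRF" and reported. It too fixes no status.

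Section 8.3.2 then plans to summarise TEAEs by, among other things, "severity, relationship to study drug, outcome, action taken and seriousness".

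**The concern.** The rule in Section 7.4.1.5 ties the status of an event to the visit at which it is identified. What decides whether an event is ongoing is whether it has ended. The two differ whenever an event starts and stops between the last two visits, because such an event first comes to light at the last visit. A brief headache two weeks before the Week 36 visit is an example: the subject reports it, the site must record it, and the rule assigns it a status that is untrue.

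What is at stake is the outcome column of the TEAE summary, and whether resolved events can be separated from persisting ones in the AE records at study end. The trial has one arm and no comparator, so a reader takes the proportion of unresolved events at face value. The analysis plan could not repair this later, because a stop date that the site was told not to enter is not in the database.

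**Working it through.** The protocol gives no figure for this point, so the check is mainly a comparison of text, with a little arithmetic for scale.

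**Step 1: which events are identified at the last visit.** The AE question in Section 7.4.1.2 covers the time since the previous visit, and every reported event must be recorded. The set therefore includes events that began and ended within that interval.

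**Step 2: how long the interval is.** Section 3.4 schedules visits every 4 weeks from Week 4 onward. Table 4 allows ±7 days at Weeks 8 to 36.

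- Nominal interval, Week 32 to Week 36: (36 − 32) × 7 = 28 days.
- Shortest, with Week 32 seven days late and Week 36 seven days early: 28 − 14 = 14 days.
- Longest, with the reverse: 28 + 14 = 42 days.

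A subject who completes early, from Week 24, also comes from 4-week spacing. After missed visits the interval is longer.

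**Step 3: what status the events receive.**

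| True state at the last visit | Status required by Section 7.4.1.5, read literally | Correct? |
|---|---|---|
| Still present | Ongoing | Yes |
| Began and resolved since the previous visit | Ongoing | No |

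The error is confined to the second row.

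**Step 4: whether another passage undoes it.** The rest of Section 7.4.1.5 provides follow-up for clinically significant abnormal test results and for clinically significant, study-related abnormalities. An ordinary AE that is already over falls under neither. Section 7.4.1.6 applies only to serious events. Section 7.2.4 names new and ongoing events as separate things and so fixes no status, but it governs the earlier visits.

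**Step 5: where it surfaces.** Section 8.3.2 lists outcome among the TEAE summaries. Assuming that ongoing on the eCRF becomes an unresolved outcome in the table, second-row events are counted as unresolved.

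**Step 6: scale.** With the 48 subjects of Section 8.1 as denominator, one affected subject moves a percentage by 1/48 = 0.0208, about 2.1 points. The number of such subjects cannot be computed, because the protocol states no AE rate and no distribution of AE duration.

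**The case against.** The strongest reply is that the intended meaning is clear enough. The sentence stands in a section on follow-up, and the rest of that section deals with matters still open at study end. An experienced site would probably take it to mean that AEs present at the last visit are closed out as ongoing. Section 7.4.1.6 also uses the idea of identification at the last contact to include unresolved events reported earlier, so the word need not mean newly elicited. This probably is the intent, and it makes the practical harm smaller. It does not change the text, which says all and must. Section 7.4.1.6 itself counts new events among those identified at the last contact.

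A second reply is that Section 9.1 has the investigator confirm that eCRF entries match the source, so a headache documented as lasting three days could not stand as ongoing. That check would help, but it puts the site between two conflicting instructions, and up to 8 sites may settle the conflict differently.

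A third reply is that the eCRF and its completion guide are not shown and may contain the right instruction. That is so, and the step from ongoing to unresolved remains an assumption.

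A reader might also infer more than the protocol supports:

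- *That the outcome of every AE found at the last visit is wrong.* Events truly ongoing at that visit are coded correctly even on the literal reading.
- *That 11% (4/36) of AEs in a Week 36 completer, or 17% (4/24) in a Week 24 completer, are miscoded.* These are the shares of follow-up time in the last interval. They bound the miscoding only if AEs are spread evenly over time, which is implausible after a single Day 1 treatment, and only those already resolved would be miscoded.
- *That a planned duration analysis is corrupted.* Section 8.3.2 lists no AE duration summary.
- *That persisting events of concern are lost at study end.* Clinically significant abnormal results and study-related abnormalities keep their own follow-up route in Section 7.4.1.5.

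**Conclusion.** The point holds as a minor wording error in a data-collection rule. Read literally, Section 7.4.1.5 gives a false status to AEs that began and resolved between the last two visits, an interval of 28 days nominally and 14 to 42 days within the visit windows. On the assumption of the usual eCRF mapping, those events are shown as unresolved in the outcome summary.

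The effect is about 2.1 points per affected subject, with 48 subjects as the denominator, and the total is unknown. It reaches one descriptive column. Incidence, severity, causality and seriousness of TEAEs are untouched, as is every efficacy endpoint, and Section 8.3.1 plans no formal hypothesis test. No overall misclassification rate can be derived from the protocol.

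**What to change.** Replace the opening sentence of Section 7.4.1.5 with a rule based on the state of the event, for example: *AEs that are unresolved at the last scheduled study visit (or Final Evaluation Visit) are recorded as ongoing; AEs reported at that visit that have already resolved are recorded with their stop date and outcome.* Carry the same instruction into the eCRF completion guide so that all sites apply it alike.

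The cost is one sentence in the protocol and one line in the guide. It adds no visit or procedure, and it leaves the follow-up provisions in the rest of Section 7.4.1.5 as they are.

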#### **7.4.1.6. Follow-up of Post-Study Serious Adverse Events**

Any SAEs that are identified on the last scheduled contact (or at early discontinuation, if applicable) must be recorded on the AE eCRF and reported to Revance or designee according to the reporting procedures outlined in [Section 7.4.1.2](#). This may include unresolved previously reported SAEs or new SAEs. The investigator should follow these SAEs until the events are resolved, or the subject is lost-to-follow-up. The investigator should continue to report any significant follow-up information to the Medical Monitor, Revance or designee and the IRB/IEC up to the point the event has been resolved. Resolution means the subject has returned to the baseline state of health, or the Investigator does not expect any further improvement or worsening of the subject's condition.

Any new SAEs reported by the subject to the investigator that occur after the last scheduled contact and are determined by the investigator to be reasonably associated with the administration of investigational product should be reported to Revance or designee and the IRB/IEC.

#### **7.4.1.7. Investigational Product Causality and Severity**

Relationship of an AE to investigational product will be assessed as follows:

- **Definite:** There is a clinically plausible time sequence between the onset of the AE and the administration of investigational product; when the event responds to withdrawal of investigational product and/or recurs with re-administration of investigational product
- **Probable:** There is a clinically plausible time sequence between the onset of the AE and the administration of investigational product; the AE is unlikely to be caused by the concurrent/underlying illness, other drugs or procedures

- **Possible:** There may or may not be a clinically plausible time sequence between the onset of the AE and the administration of investigational product and a cause cannot be ruled out
- **Unrelated:** There is not a temporal or causal relationship to investigational product administration

The investigator is responsible for evaluating all AEs and determining the severity of the event. Severity will be categorized as mild, moderate or severe according to the following definitions:

- **Mild:** Event may be noticeable to subject; does not influence daily activities; usually does not require intervention
- **Moderate:** Event may be of sufficient severity to make subject uncomfortable; performance of daily activities may be influenced; intervention may be needed
- **Severe:** Event may cause severe discomfort; usually interferes with daily activities; subject may not be able to continue in the study; treatment or other intervention usually needed

#### 7.4.2. Physical Examination

A targeted physical examination. [REDACTED] will be conducted. Significant physical examination findings that are present prior to investigational product administration are to be included on the Medical History eCRF.

Significant physical examination findings after investigational product administration, which meet the definition of an AE, will be recorded on the AE eCRF post-treatment.

#### 7.4.3. Vital Signs

Vital signs (i.e., body temperature, respiration rate, sitting radial pulse rate, and sitting systolic and diastolic blood pressures) will be obtained. Subjects must sit for 5 minutes prior to having pulse and blood pressure measurements taken. Any new abnormal findings or worsening from baseline at subsequent assessments, if judged clinically significant, should be recorded as an AE on the AE eCRF page.

[REDACTED]

#### 7.4.4. Pregnancy Testing

A UPT is required for all WOCBP at screening, baseline (pre-treatment) and Week 36 or Final Evaluation Visit. A positive result prior to treatment will exclude the subject from study participation. The results of the UPT will be evaluated at each study center. If any subject has a positive UPT after treatment, a serum pregnancy test is required for confirmation.

If a female subject becomes pregnant while participating in the study, the investigator or site designee must complete the Pregnancy Report Notification Form provided by Revance or designee as soon as the pregnancy is confirmed ([Section 4.6](#)).

#### 7.4.5. Injection Site Evaluation

Injection sites will be evaluated at screening to assess for skin inflammation or active skin disease and at later timepoints to determine if there is an immediate reaction to the investigational product. The assessment will be done as a global evaluation of the 5 GL injection sites, the 4 FHL injection sites, and each of the 3 injection sites for LCL on each side of the face. Refer to [Appendix 13](#).

**Table 12** **Injection Site Evaluation**

Assessment Descriptor	Present?	
	Yes	No
Erythema		
Edema		
Burning or Stinging (sensation as described by subject)		
Itching (sensation as described by subject)		
Bruising		

If the subject answers yes to any of these items, it should be captured and recorded as an AE.

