### 7.4.1. Adverse Events and Serious Adverse Events

#### 7.4.1.1. Evaluation of Adverse Events and Serious Adverse Events

For this protocol, an **adverse event (AE)** is any untoward medical occurrence (e.g., sign, symptom, disease, syndrome, intercurrent illness, clinically significant abnormal laboratory finding, injury or accident) that emerges or worsens following administration of investigational product and until the end of study participation that may not necessarily have a causal relationship to the administration of the investigational product. An AE can therefore be any unfavorable and/or unintended sign (including a clinically significant abnormal laboratory result), symptom, or disease temporally associated with the use of an investigational product, whether or not considered related to the investigational product. A treatment-emergent AE is one that occurs after any period of exposure to treatment.

Pre-existing conditions, which increase in frequency or severity or a change in nature as a consequence of an investigational product use will also be considered an adverse event.

An unexpected AE is an adverse reaction, the nature or severity of which is not consistent with the applicable product information (e.g., Investigator's Brochure for an unapproved investigational product or package insert/summary of product characteristics for an approved product).

Any change in the study safety evaluations, (e.g., vital signs, injection site evaluation) post-treatment determined to be clinically significant by the investigator must be reported as an AE.

An **SAE** is any untoward medical occurrence that results in any of the following outcomes:

- Death

- Life-threatening, (i.e., the subject was, in the opinion of the Investigator, at immediate risk of death from the event as it occurred. It does not apply to an AE that hypothetically might have caused death if it were more severe)
- Persistent or significant disability/incapacity or substantial disruption of the subject's ability to carry out normal life functions
- Requires in-patient hospitalization or prolongs hospitalization (i.e., a prolonged hospitalization beyond the expected length of stay; hospitalizations for elective medical/surgical procedures, scheduled treatments, or routine check-ups are not SAEs by this criterion)

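### Sections 7.4.1.1 and 7.4.5 set different thresholds for recording an injection-site finding as an adverse event, so TEAE incidence could depend on which section a site follows

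*Protocol*

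**What the plan says.** Section 7.4.1.1 of the protocol deals with changes in the safety evaluations and gives the injection site evaluation as one of two examples. The sentence runs, in part: "e.g., vital signs, injection site evaluation) post-treatment determined to be clinically significant by the investigator must be reported as an AE".

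Section 7.4.5 describes the evaluation itself. Table 12 lists erythema, edema, burning or stinging, itching and bruising, each answered yes or no. The rule below the table is: "If the subject answers yes to any of these items, it should be captured and recorded as an AE". It mentions neither clinical significance nor timing.

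The evaluation is not confined to the period after treatment: "Injection sites will be evaluated at screening to assess for skin inflammation or active skin disease and at later timepoints". The adverse event definition in 7.4.1.1, by contrast, covers an occurrence "that emerges or worsens following administration of investigational product and until the end of study participation".

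Two nearby provisions bear on the same records. Section 7.4.1.2 states two collection windows: "All AEs (serious and non-serious) will be collected from the signing of the ICF until the Final Evaluation Visit" and, in the next paragraph, "All AEs will be collected after IP administration until Week 36 or the Final Evaluation Visit". Section 7.4.1.5 says that adverse events identified at the last scheduled visit "must be recorded on the AE eCRF as ongoing".

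**The concern.** The same finding, say mild bruising on Day 1 that the investigator considers trivial, is an adverse event under Table 12 and need not be one under the clinical-significance sentence in 7.4.1.1. No visible text says which provision governs. Vital signs (7.4.3) and laboratory values (7.4.6) both use clinical significance, so a site could read Table 12 either as a deliberate exception or as subject to the same filter.

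Safety is part of the primary objective. Section 3 lists the incidence, severity and relationship of TEAEs among the safety evaluations, and Section 8.3.2 counts subjects with events. The study has one arm and no placebo comparator (8.3.1). A recording difference therefore cannot cancel between arms and passes straight into the reported incidence.

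**Working it through.** **Setting the rules side by side**

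- Trigger. 7.4.1.1: the investigator's judgement of clinical significance. Table 12: any 'yes'.
- Timing. 7.4.1.1: post-treatment change. Table 12: no limit, with the evaluation also done at screening.
- Compatibility. 7.4.1.1 makes significant changes mandatory adverse events. It does not say that only those are adverse events. Recording every post-treatment 'yes' satisfies both. However, if Table 12 governs, the filter in 7.4.1.1 has no function for this evaluation.

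**What can be affected**

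- Injection-site TEAEs, the overall TEAE incidence that includes them, and their severity and relationship tabulations can be affected.
- Pre-dose findings and the choice of collection window do not change TEAE counts, because 7.4.1.1 and 8.3.2 both define treatment emergence from treatment onward. They change only which adverse event records exist.
- SAEs have their own criteria, and the efficacy endpoints use other scales.

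**Illustration of size**

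The protocol states no TEAE rate, so there is no figure to reproduce. From the protocol: N = 48 (8.1) and 8 sites (3.1; the synopsis says up to 8). One subject is 100/48 = 2.1 percentage points. Two inputs are assumed: p, the share of subjects with any post-treatment 'yes', and s, the share of those judged clinically significant.

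Incidence from this source is p under the any-'yes' rule and p × s under the clinical-significance rule. The gap is p × (1 − s). With counts rounded to whole subjects (halves to the even number) and exact 95% intervals for the any-'yes' rule:

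| Any 'yes' | Any-'yes' rule | s = 10% | s = 25% | s = 50% | s = 100% |
|---|---|---|---|---|---|
| 5/48 | 10.4% (3.5 to 22.7) | 0/48 = 0.0% | 1/48 = 2.1% | 2/48 = 4.2% | 5/48 = 10.4% |
| 12/48 | 25.0% (13.6 to 39.6) | 1/48 = 2.1% | 3/48 = 6.25% | 6/48 = 12.5% | 12/48 = 25.0% |
| 24/48 | 50.0% (35.2 to 64.8) | 2/48 = 4.2% | 6/48 = 12.5% | 12/48 = 25.0% | 24/48 = 50.0% |

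The rules agree only when s = 100%. At s = 0 the gap is the whole of p: 10.4, 25.0 or 50.0 points.

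If k of 8 equal-sized sites use clinical significance, the expected pooled incidence is p × [(8 − k)/8 + (k/8) × s]. With p = 25% and s = 10%:

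- k = 0: 25.0%
- k = 4: 25 × (0.5 + 0.5 × 0.1) = 13.75%, or 13.8%
- k = 8: 2.5%

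These figures show how the result responds to the rule. They do not predict this trial.

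**The case against.** **The sentences do not contradict each other outright.** A reader might infer that they do. They do not: Table 12 is the specific instruction for this evaluation, and following it after treatment also satisfies 7.4.1.1. The general definition in 7.4.1.1 also takes in any unfavorable sign or symptom and attaches clinical significance only to laboratory findings, so a careful site could record mild bruising under 7.4.1.1 as well. This stands, and it limits the point to differing thresholds and an avoidable ambiguity.

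**Screening findings and the two windows cannot inflate TEAE incidence.** This stands too. TEAEs are defined from treatment, and exclusion criterion 3 removes subjects with active skin conditions at the injection sites. A further sentence in 7.4.1.2 partly bridges the windows by admitting pre-treatment occurrences related to protocol-mandated intervention.

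**The raw findings are reported anyway.** Section 8.3.2 plans a separate summary of injection site findings, and TEAEs are tabulated by preferred term. Readers can therefore isolate these events, and no extra safety table is needed. But Table 12 holds only presence or absence. The severity and relationship gradings in 7.4.1.7 belong to adverse events, and the TEAE incidence itself would still follow whichever rule a site used.

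**Clarifying text may exist out of sight.** Appendix 13, the schedule of assessments and part of Section 7.4.1 are not visible in the public document. That is possible, but the two visible sentences would still need to be aligned.

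**Conclusion.** The point holds as a mismatch of recording thresholds. Injection-site TEAE incidence, and the overall TEAE incidence with it, could depend on whether a site works from 7.4.1.1 or 7.4.5. The effect may be zero, if every site records every post-treatment 'yes' or if every 'yes' is judged clinically significant. Its actual size cannot be derived from the protocol, and every rate in the illustration is assumed.

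Three stronger readings are not supported. The protocol does not show that sites will in fact apply different thresholds. It does not say that injection-site reactions are the most frequent event type. Nor does a tenfold difference between the rules follow from it, since that ratio is simply 1/s with s assumed to be 10%.

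The two collection windows in 7.4.1.2 are a real but secondary defect. So is the 'ongoing' rule in 7.4.1.5: read literally, it gives the wrong outcome for an event first identified at the last visit but already resolved. That can misstate the outcome field for such events, which 8.3.2 tabulates. Neither changes TEAE incidence.

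**What to change.** Reconcile 7.4.1.1 and 7.4.5 to one recording rule. One way is to take injection site evaluation out of the clinical-significance sentence in 7.4.1.1 and limit the Table 12 rule to post-treatment 'yes' answers that are new or worsened, with pre-dose findings recorded as medical history. Because Table 12 records presence only, worsening of a pre-existing finding would need the investigator's judgement.

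As secondary tidying, state one adverse event collection window in 7.4.1.2, and reword 7.4.1.5 so that only adverse events unresolved at the last visit are recorded as ongoing.

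The cost is a few clarified paragraphs and a memo to sites. The downside of the any-'yes' rule is that the reported TEAE rate may be higher.
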